#### **9.4.3. Secondary Endpoints**

Analysis of dose dependency for brensocatic  $AUC_{0-24}$ ,  $AUC_{last}$ , and  $C_{max}$  after single- and multiple-dose administration will be performed using a power law model. The log-transformed PK parameters will be regressed onto log-transformed dose. An estimate of the slope and corresponding 95% CI will be reported. In addition, pairwise comparisons of dose dependency among brensocatic dose levels may be performed based on dose-normalized  $AUC_{0-24}$ ,  $AUC_{last}$ , and  $C_{max}$  for Day 1 and Day 28. The details of the analysis will be included in the SAP.

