Note: Assumes N=number of participants treated with brensocatic per dose group.
gCV% = geometric coefficient of variation percentage, CI = confidence interval, GM = geometric mean, LL = lower limit, UL = upper limit.

Table 3: 95% CIs for Values of Inter-Participant gCV% of the AUC_{0-24} and C_{max} GM for Each Stratum Within Each Actively Treated Cohort

gCV%	GM 95% CI LL	GM 95% CI UL
30	GM÷1.440	GM×1.440
40	GM÷1.613	GM×1.613
50	GM÷1.798	GM×1.798

Note: Assumes N=5 (number of participants treated with brensocatic per stratum in each dose group).

The range of values for gCV% is based on the results of Day 29 AUC_{last} and C_{max} in a study of patients with non-cystic fibrosis bronchiectasis (NCFBE) (INS1007-201) and on the results of Day 28 AUC_{0-24} and C_{max} in a multiple-dose study of healthy volunteers (D6190C00001).

For the primary evaluation of safety, N=10 or 7 participants per brensocatic dose group provides 80% or 68% probability, respectively, to detect an adverse event (AE) that occurs with an incidence rate of 15%, and 90% or 80% probability, respectively, to detect an AE that occurs with an incidence rate of 21%.

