7. GENERAL STATISTICAL CONSIDERATIONS

7.1. General

Tables and figures will be provided by treatment group/dose level (10 mg, 25 mg, 40 mg, and 65 mg [if conducted] QD brensocatic, pooled placebo except for PK output). If sample sizes permit, summaries will be further stratified by CFTR modulator and non-modulator.

Treatment arm/dose levels will be presented in this stratified analysis if the number of observations is ≥ 2 . If the assignment to a stratum differs between the randomization file and the eCRF, the randomization file will prevail. In the listings, CFTR modulator use will be indicated by + for participants on CFTR modulator and by - for the non-modulator stratum following the Subject Identifier. For tables in the demographic and safety sections, also a Total column will be presented.

Descriptive statistics for continuous variables will be calculated at scheduled visits (nominal timepoints for PK) and will include the number of participants in the treatment group/dose level of the respective analysis set (N in column header of the table), the number of non-missing- observations (n), the number of observations below limit of quantification (BLQ) for PK and PD tests, arithmetic mean, standard deviation (SD), median, minimum, and maximum. For brensocatic plasma concentrations, the GM with 95% CI and gCV%, for PK parameters (except for t_{\max} and t_{last}), and PD tests, the GM and gCV% will be reported in addition. The GM will be derived by calculating the arithmetic mean of the natural log-transformed observations and then back-transforming the mean by exponentiation. The gCV% will be calculated as: $100 \times \sqrt{\exp[\text{variance of the log-transformed values}] - 1}$. GM and gCV% will only be calculated for quantifiable values above 0. For t_{\max} and t_{last} , only n, median, minimum, and maximum will be presented. For PK parameters, no descriptive statistics will be calculated when fewer than three individual PK parameter values are available. Summaries of continuous variables other than plasma concentrations that have some values recorded using approximate values (e.g., $<$ or $>$) will use the numeric part of the value in calculations. Rules for plasma concentrations BLQ or missing are given in [Section 11](#).

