9.1. Spirometry

Spirometry tests include the following: prebronchodilator FEV₁, prebronchodilator ppFEV₁, FVC, and FEF_(25-75%).

Observed values and change from baseline at Day 28 will be summarized descriptively by scheduled visit. If applicable (more than 5 participants who prematurely discontinued the study) a separate analysis using the end of treatment (EoT) assessment, i.e., Day 28 or Early Discontinuation, will be done.

An analysis of covariance will be performed for change from baseline at Day 28 including the baseline value in the model as fixed covariate and the treatment group/dose level as fixed factor. The analysis will be stratified by CFTR modulator / non-modulator if sample sizes permit (see [Section 7.1](#)). Least Squares (LS) means for each treatment group and dose levels with 95% CIs and LS mean differences between each Brensocatib dose level and placebo with 95% CIs will be provided.

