11.1.3. Assessment of Dose Proportionality

Analysis of dose dependency for brensocatic AUC_{0-24} , AUC_{last} , and C_{max} after single-dose administration and at steady state (Day 28) will be performed using a power law model². The logarithm of the PK parameter will be linearly related to the logarithm of the dose using a linear regression analysis in the following way:

$$\ln(PK) = \beta_0 + \beta_1 \cdot \ln(\text{dose}),$$

where $\ln(PK)$ represents the natural log transformed AUC_{0-24} , AUC_{last} , and C_{max} parameter and $\ln(\text{dose})$ represents the natural log transformed dose as fixed factor.

LS estimates of the slope of the regression and corresponding 90% CIs will be obtained.

Dose proportionality plots for C_{max} , AUC_{0-24} , and AUC_{last} at Day 1 (after single dose administration) and at Day 28 (after multiple dose administration): the natural log-transformed PK parameter versus natural log-transformed dose will be displayed with the fitted line from the power law model. The individual natural log-transformed data will be displayed around the fitted line. The CFTR modulator / non-modulator groups will be displayed on the same plot.

A categorical covariate for CFTR modulator stratum or separate analyses by stratum may be conducted if the C_{max} , AUC_{0-24} , and AUC_{last} values between strata are dissimilar, as assessed by visual inspection of the above dose proportionality plots for C_{max} , AUC_{0-24} , and AUC_{last} parameters. A clear separation of the individual data for CFTR modulator / non-modulator groups suggests dissimilarity in the PK profile between the two CFTR strata. Analyses will be repeated for brensocatic PK parameters after multiple-dose administration on Day 28.

In addition, pairwise comparisons of dose dependency among brensocatic dose levels may be performed based on dose-normalized C_{max} , AUC_{0-24} , and AUC_{last} separately for Day 1 and Day 28. An analysis of variance will be run with the natural-log transformed ratio of the PK parameter divided by the dose as dependent variable and the dose level as independent fixed effect. The LS means and LS mean difference will be back transformed to obtain the geometric means and ratio of geometric means along with corresponding 90% CI. If dose proportionality holds between the 2 dose levels being compared, the ratio of geometric means will be approximately 1.00.

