If dose proportionality applies, data within stratum (CFTR modulator and non-modulator) will be pooled across dose levels. The log-transformed dose-adjusted C_{max} , AUC_{0-24} , and AUC_{last} for Day 1 and Day 28 will be used as dependent variable in an analysis of variance with the CFTR stratum as independent variable. The LS mean for the difference between strata with 90% CI will be estimated from the model. The estimate and lower and upper confidence limits will be back transformed by exponentiation. The back-transformed difference between the strata is the GM ratio of the strata.

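### SAP 11.1.3 makes both routes to a CFTR-stratum estimate of exposure conditional on undefined criteria; one power model with a stratum term would need neither

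*SAP*

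**What the plan says.** - **Power model (SAP 11.1.3).** Log PK parameter is regressed on log dose alone, for AUC0-24, AUClast and Cmax on Day 1 and Day 28. A stratum covariate, or separate analyses by stratum, is optional if the strata look dissimilar, "assessed by visual inspection of the above dose proportionality plots". The only guide is that "A clear separation of the individual data for CFTR modulator / non-modulator groups suggests dissimilarity". No amount of overlap is specified, and the choice between covariate and separate models is left open.
- **Between-strata comparison (end of SAP 11.1.3).** "If dose proportionality applies, data within stratum (CFTR modulator and non-modulator) will be pooled across dose levels". An analysis of variance of the dose-adjusted log parameters on stratum then gives a GM ratio with a 90% CI. Protocol 9.4.1 likewise foresees a dose-normalised comparison and makes pooling optional, subject to approximate proportionality. Neither document says how proportionality is judged. The nearest text is a remark on the optional pairwise dose comparisons, that the ratio should be near 1; it has no limits.
- **Slope CI.** Protocol 9.4.3: "An estimate of the slope and corresponding 95% CI will be reported". SAP 11.1.3 uses 90%. SAP 13 declares no changes to protocol-specified analyses.
- **By-dose summaries within stratum.** Protocol 9.2 and SAP 4.2 promise AUC0-24 and Cmax GMs by dose within each stratum. The plan has 2 non-modulators per dose. SAP 7.1 says of PK parameters that "no descriptive statistics will be calculated when fewer than three individual PK parameter values are available". The same section has a general display rule, "Treatment arm/dose levels will be presented in this stratified analysis", with a threshold of two observations.
- **Stratum precision table (Protocol Table 6, SAP Table 3).** The title refers to each stratum, and the note reads "Assumes N=5 (number of participants treated with" brensocatib per stratum in each dose group.
- **Spirometry (SAP 9.1).** "The analysis will be stratified by CFTR modulator / non-modulator if sample sizes permit". SAP 9.2 allows the same for CFQ-R.

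**The concern.** The plan stratifies on CFTR status, Protocol 9.4.1 foresees an exposure comparison between strata, and SAP 5.1 accepts that the maximum tolerated dose may differ by modulator use. A reader would therefore expect a between-strata exposure ratio to be reported whatever the data look like. Under SAP 11.1.3 it is not guaranteed. Whether the analysis of variance runs depends on a judgement about the dose slope, which is a different question from the stratum effect. If that judgement goes the wrong way, everything rests on someone's view of a scatter plot. Two analysts with the same data could then differ on whether any stratum estimate appears in the report.

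**Working it through.** **Inputs**
- 5 modulator and 2 non-modulator participants per active dose (SAP Table 1): 15 vs 6 over three doses, 20 vs 8 over four.
- CV 30, 40 and 50% (SAP Tables 2 and 3). σ = √ln(1+CV²) = 0.2936, 0.3853, 0.4724.
- True stratum ratios of 1.25, 1.5 and 2.0 are assumptions; the documents give none.

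**1. Reproducing the plan's own figure.** The CI factor for a GM is exp(t × σ/√N), with t the 0.975 quantile on N−1 df. For N=5, t = 2.776 and the factors are 1.440/1.613/1.798, matching SAP Table 3. For N=2, the planned non-modulator cell, t = 12.706 and the factors are 14.0/31.9/69.7.

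**2. The planned analysis of variance, when it runs (15 vs 6, 19 df).** SE = σ√(1/15+1/6) = 0.483σ. With t = 1.729, the 90% CI factor on the GM ratio is exp(1.729 × 0.483σ) = 1.28/1.38/1.48. The probability that the CI excludes 1 comes from the noncentral t distribution; for a 1.5-fold ratio at CV 30% the noncentrality is 0.4055/(0.483 × 0.2936) = 2.86.

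| True ratio | Planned ANOVA, CV 30/40/50% | Power model with stratum term (18 df) |
|---|---|---|
| 1.25 | 45/32/25% | 45/31/24% |
| 1.5 | 87/68/53% | 87/67/53% |
| 2.0 | 99.9/97/90% | 99.9/97/90% |

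The two are equivalent for detection. With 20 vs 8 the ANOVA gives 94/79/64% at 1.5-fold.

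**3. How well proportionality can be judged.** At ln 10, ln 25 and ln 40 the squared deviations from their mean sum to 0.994. With 7 per dose, Sxx = 7 × 0.994 = 6.96. The slope's 90% CI half-width is 1.729σ/√6.96 = 0.19/0.25/0.31. With 65 mg added it is 0.14/0.18/0.22. An unmodelled 1.5-fold stratum effect widens the three-dose half-width to 0.23/0.28/0.33.

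The SAP gives no rule, so suppose proportionality were rejected when the 90% CI for the slope excludes 1. With a true slope of 0.8 and a 1.5-fold stratum effect, it would be rejected in about 24% (CV 50%) to 41% (CV 30%) of three-dose trials. In those trials the between-strata ANOVA would not be triggered.

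**4. The visual check as the only remaining route (simulation, three doses, CV 30/40/50%).**

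| Reading of clear separation | 1.5-fold | 2-fold |
|---|---|---|
| No overlap across all dose-adjusted values | 1.9/0.6/0.2% | 23/7/3% |
| No overlap within any dose | 5.5/1.9/0.9% | 39/15/7% |
| All six non-modulators beyond the modulator median | 58/40/29% | 93/78/62% |

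For a 1.5-fold effect at CV 30%, the trigger fires in anything from 2% to 58% of trials, depending only on how the phrase is read.

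**5. Bias.** With 5:2 at every dose, stratum and log dose are uncorrelated. Omitting stratum does not bias the slope; it inflates the residual variance. By the same balance, a slope other than 1 does not bias a stratum ratio common to all doses, so proportionality is not needed as a precondition for estimating that ratio.

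**The case against.** The strongest reply is that SAP 11.1.3 already contains the stratum analysis. A reader who stops at the visual rule might infer that stratum reaches a PK model only after visible separation, so that a real modulator effect would almost always be missed. The documents do not support that. The analysis of variance does not depend on the visual check, and when it runs it performs as well as the model proposed here. Percentages near zero apply only to the visual route alone, under a strict no-overlap reading that the SAP never states.

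Other points on that side:
- Protocol 4.3 reports similar conclusions of dose proportionality in earlier work, so the condition may well be met. The SAP also cites a methods paper on confidence-interval criteria for dose proportionality. Both are fair, but the plan adopts no limits from that paper.
- No listed objective concerns the effect of modulators on exposure, and SAP 7.3 disclaims inferential conclusions. This limits the importance of the point. It does not remove the need to specify an estimate that the plan intends to report.
- Suppressing cells of two is sensible, given CI factors of 14 to 70. Individual values are still listed and both strata are plotted. What remains is that the promised by-dose non-modulator GMs will not be produced.
- The text of Protocol 9.2 and SAP 4.2 does limit the N=5 table to the modulator stratum; only its title and note are loose.
- The stratified spirometry and CFQ-R models are conditional or optional, so a sparse non-modulator model is not a committed analysis.
- SAP 2 says the SAP prevails over the protocol, which settles which slope CI level applies. It does not explain why SAP 13 is silent.

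**Conclusion.** The point holds as a gap in pre-specification. It does not show that the planned comparison is weak. If proportionality is accepted, the planned ANOVA is adequate for differences of 1.5-fold (53 to 87%) or 2-fold (90% or more). A 1.25-fold difference is usually missed (25 to 45%), because of sample size, and the fix does not change that. If proportionality is rejected, no stratum estimate is guaranteed. That could happen in about 24 to 41% of three-dose trials under one illustrative rule, a true slope of 0.8 and a 1.5-fold stratum effect. These figures assume log-normal data, CVs of 30 to 50%, the planned 5:2 balance and a stratum ratio constant across doses. The slope CI mismatch is real and undeclared. The table label and the suppressed cells are secondary.

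**What to change.** 1. For Cmax, AUC0-24 and AUClast on Day 1 and on Day 28, always fit ln(PK) = b0 + b1·ln(dose) + b2·stratum. Report b1 and exp(b2) with CIs. Remove the visual trigger and the proportionality condition; keep the plots as description.
2. Choose one CI level for the slope and, if it differs from the protocol's 95%, declare the change in SAP 13.
3. Where the spirometry and CFQ-R models are fitted, include stratum as a fixed factor instead of running separate models by stratum.
4. Retitle Protocol Table 6 and SAP Table 3 as the CFTR modulator stratum (N=5). State that non-modulator cells of two fall under the fewer-than-three rule, so their by-dose GMs will not be reported, and say how that rule sits with the two-observation display rule.

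The cost is SAP wording, a few lines of code and one residual degree of freedom: 19 to 18 in the three-dose power model, where the 90% slope half-width at CV 30% stays at 0.19 (1.734 × 0.2936/√6.96). No new data are needed.

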11.1.4. Pharmacokinetic-Pharmacodynamic Analysis

Additional PK-PD evaluations will be specified in a separate PK/PD Analysis Plan:

- To evaluate the PK/PD relationship between AUC/dose and biomarker activity (blood and/or sputum),
- To evaluate the PK/PD relationship between systemic exposure and safety (e.g., AESIs of hyperkeratosis, periodontitis/gingivitis, and infections),
- To evaluate the PK/PD relationship between systemic exposure and clinical efficacy (i.e., ppFEV₁ and CFQ-R).

12. PHARMACODYNAMICS

For the general layout of the tables see [Section 7.1](#).

PD Tests NE, CatG, and PR3 will be assessed in blood and in sputum. Baseline is defined in [Section 7.1](#). The most recent non-missing value before the first dose of IP will be used as baseline which is either the assessment at Day 1 pre-dose or if this is not available the assessment at Screening. If both assessments are not available, the participant will not be included in the PD analysis set.

The strategies for the ICEs as outlined in [Section 3.3](#) and [Section 7.2](#) will be applied.

Descriptive statistics (including GM and gCV% for observed values and number of values BLQ) will be provided for observed values and %inhibition from baseline by scheduled visit (on natural scale). %Inhibition from baseline will be calculated as $100 * (1 - \text{fold change from baseline})$, where $\text{fold change} = \text{post baseline value} / \text{baseline value}$. Observed values that are BLQ will be set to 0 in the calculation of descriptive statistics. If sample protein concentration data are available, the activity of NE, CatG and PR3 should be normalized by the protein concentration, to generate activity values of ng/ml/mg protein, and the normalized NSP data will be presented in the same way as described above.

The neutrophil count summary will be included in the safety (hematology) analyses.

The following figures will be provided for each PD test for concentrations in blood and in sputum:

- Mean (+/- SD) over time using scheduled sampling time on natural scale by dose level overlaid in the same figure.
- Mean %inhibition (+/- SD) values over time using scheduled sampling time by dose level overlaid in the same figure.
- Individual participant profiles for PD data over time at scheduled visits – the participant's dose levels will be distinguished by different colors (spaghetti plots).

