### 3. OBJECTIVES AND ENDPOINTS

Objectives	Endpoints
Primary	
To evaluate the PK of brensocatic in participants with CF following once daily oral administration of study drug	$C_{max}$ , $t_{max}$ , $AUC_{0-24}$ , and $t_{1/2}$ on Day 1 and Day 28
To evaluate the safety of brensocatic compared to placebo in participants with CF over the 4-week treatment period	Frequency of treatment-emergent adverse events a
Secondary	
To evaluate the dose-dependency of brensocatic exposure	$C_{max}$ , $AUC_{0-24}$ , and $AUC_{last}$ on Day 1 and Day 28
Exploratory	
To evaluate the effect of brensocatic compared with placebo on the concentration of NE, CatG, and PR3 in sputum over the 28 day treatment period	Change from Baseline to Day 14, Day 28, and over the 28 day treatment period for concentration of NE, CatG, and PR3 in sputum
To evaluate the effect of brensocatic compared with placebo on the concentration of NE, CatG, and PR3 in blood over the 28 day treatment period	Change from Baseline to Day 14, Day 28, and over the 28 day treatment period for concentration of NE, CatG, and PR3 in blood
To assess the effect of brensocatic compared with placebo on lung function, as measured by change in pulmonary function parameters, including ppFEV 1 , FEV 1 , FVC, and FEF (25-75%) at Day 28	Change from Baseline to Day 28 in ppFEV 1 , FEV 1 , FVC, and FEF (25-75%)
To evaluate the effect of brensocatic compared with placebo on quality of life as measured by CFQ-R through Week 4	Change from Baseline to Day 14 and Day 28 for the CFQ-R Respiratory Domain score

Objectives	Endpoints
To evaluate the PK/PD relationship between AUC/dose and biomarker activity (blood and/or sputum)	NE, CatG, and PR3 concentrations between Day 14 and Day 28 in blood and sputum vs. brensocatib exposure at steady state
To evaluate the PK/PD relationship between systemic exposure and safety (eg, AESIs of hyperkeratosis, periodontitis/gingivitis, and infections)	AESIs during the 28-day treatment period and their relationship to brensocatib exposure at steady state
To evaluate the PK/PD relationship between systemic exposure and clinical efficacy (ie, ppFEV 1 and CFQ-R)	ppFEV 1 and CFQ-R during the 28-day treatment period and their relationships with brensocatib exposure at steady state

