### 9.4.1. General Considerations

There is no hypothesis-testing in this study, and no inferential statistical analyses will be conducted. There will be no proxy values for missing data. PK, PD, and efficacy data will be presented in tables, listings, and graphs as appropriate for each variable. All data will be summarized by treatment group (dose levels of brensocatib and pooled placebo) and by treatment group within strata (CFTR modulator and non-modulator) if data warrant. The  $C_{\max}$  and AUC data may be pooled data across all dose levels within each stratum if the systemic exposure is approximately dose proportional, and the exposure difference between CFTR and non-CFTR participants will be compared based on dose-normalized  $C_{\max}$  and AUC. Data from placebo participants will be excluded from PK evaluation.

PK parameters, such as  $C_{\max}$ ,  $t_{\max}$ ,  $C_{\min}$ ,  $AUC_{0-24}$ ,  $AUC_{\text{last}}$ ,  $AUC_{0-\infty}$ ,  $CL/F$ ,  $Vd/F$ ,  $t_{1/2}$ ,  $R_{ac}(C_{\max})$ , and  $R_{ac}(AUC)$ , will be derived using non-compartmental analysis, as appropriate.  $C_{\text{trough}}$ , the predose levels on Day 2, Day 14, Day 28, and Day 29, will be listed and summarized using descriptive statistics based on nominal timepoints.

The frequency of TEAEs is the primary safety endpoint for this study. All safety analyses will be performed on the safety population. AE listings will be produced. TEAEs, SAEs, AEs leading to treatment and/or study withdrawal, and AESIs will be listed for each participant along with outcome, severity, and relatedness to study IMP. Ad hoc summaries of TEAEs may be prepared if the volume of data allows.

Exploratory endpoints include PD markers (NE, CatG, and PR3 in sputum and in blood), FEV1, and CFQ-R Respiratory Domain Score. In addition, the relationship between brensocatib exposure and NE activity will be explored.

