#### **9.4.4. Exploratory Endpoints**

NE, CatG, and PR3 (in sputum and in blood) will be exploratory endpoints. The results of these parameters will be listed by participant and timepoint and summarized by treatment group (dose levels of brensocatic and pooled placebo) and by treatment group within strata (CFTR modulator and non-modulator, pooled data across all dose levels). Where sufficient sample sizes are achieved (ie, adequate sample obtained and minimum number of quantifiable concentrations), a linear model with appropriate covariance pattern will be fit to the exploratory endpoints and between-group comparisons with associated 95% CIs will be reported.

Individual figures of NE, CatG, and PR3 versus time will be presented with all participants overlaid on the same plot for each dose level (spaghetti plots). Mean plots versus time will also be presented by treatment group (dose levels of brensocatic and pooled placebo) and by treatment group within each stratum (CFTR modulator and non-modulator).

FEV1 and CFQ-R Respiratory Domain are also exploratory endpoints. These variables will be listed and summarized in tables by brensocatic dose levels and placebo.

The relationship between dose and the 3 PD parameters (NE, CatG, and PR3) will be displayed graphically.

Additional PK-PD evaluations will be performed in separate analyses, in which the relationship between brensocatic exposure (dose or AUC) and clinical measurements (PD biomarkers, ppFEV1 and AESI) will be explored. The results from these PK-PD analyses will be reported separately.

Microbial species and colony forming units from sputum assessments will be listed and summarized by brensocatic dose levels and placebo.

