3.3. Exploratory Objectives and Estimands

Pharmacodynamic Objective(s)	
To evaluate the effect of brensocatib compared with placebo on the concentration of Neutrophil Elastase (NE), Cathepsin G (CatG), and Proteinase 3 (PR3) in sputum over the 28-day treatment period	
Population	Participants with CF defined by the inclusion and exclusion criteria of the CSP
Treatment Regimen	1 tablet QD of brensocatib or placebo (actual treatment)
Endpoints	Percentage inhibition from baseline to Day 14 and Day 28 for concentration of NE, CatG, and PR3 in sputum
Population Level Summary	Treatment means for observed values and for percent inhibition from baseline
ICE	
 • Early discontinuation from randomized IP for any reason, • Use of antibiotics during an acute event that could affect neutrophil serine protease (NSP) levels
Strategy	The While-On-Treatment strategy (including up to Day 35 follow-up period) will be applied for both ICEs.

Pharmacodynamic Objective(s)	
To evaluate the effect of brensocatib compared with placebo on the concentration of NE, CatG, and PR3 in blood over the 28-day treatment period	
Population	Participants with CF defined by the inclusion and exclusion criteria of the CSP

Treatment Regimen	1 tablet QD of brensocatib or placebo (actual treatment)
Endpoints	Percentage inhibition from baseline to Day 14 and Day 28 for concentration of NE, CatG, and PR3 in blood
Population Level Summary	Treatment means for observed values and for percent inhibition from baseline
ICE	
 • Early discontinuation from randomized IP for any reason, • Use of antibiotics during an acute event that could affect NSP levels
Strategy	The While-On-Treatment strategy (including up to Day 35 follow-up period) will be applied for both ICEs.

Efficacy Objective(s)	
To assess the effect of brensocatib compared with placebo on lung function, as measured by change in pulmonary function tests including ppFEV ₁ , FEV ₁ , FVC, and FEF _(25-75%) at Day 28	
Population	Participants with CF defined by the inclusion and exclusion criteria of the CSP
Treatment Regimen	1 tablet QD of brensocatib or placebo (randomized treatment)
Endpoints	Change from Baseline to Day 28 in prebronchodilator ppFEV ₁ , FEV ₁ , FVC, and FEF _(25-75%)
Population Level Summary	Treatment means or difference in means if data allow estimation based on a statistical model

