13. CHANGES TO PROTOCOL-SPECIFIED ANALYSES

Currently, no changes from the protocol-specified analyses are planned.

A Screened Analysis Set was defined in [Section 6.1](#) in addition to the analysis sets defined in the CSP.

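### The SAP omits, without declaring it, the protocol's conditional model-based comparison of NE, CatG and PR3 with placebo, and takes the arithmetic mean of % inhibition as its main PD summary

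*SAP*

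**What the plan says.** **Protocol.** The sputum objective in section 3 is comparative: "To evaluate the effect of brensocatic compared with placebo on the concentration of NE, CatG, and PR3 in sputum over the 28 day treatment period". The blood objective matches it. The endpoint has three parts: "Change from Baseline to Day 14, Day 28, and over the 28 day treatment period for concentration of NE, CatG, and PR3 in sputum". For the analysis, section 9.4.4 sets a condition, "Where sufficient sample sizes are achieved (ie, adequate sample obtained and minimum number of quantifiable concentrations", and then commits: "a linear model with appropriate covariance pattern will be fit to the exploratory endpoints and between-group comparisons with associated 95% CIs will be reported". Section 9.4.1 limits how far this goes: "There is no hypothesis-testing in this study, and no inferential statistical analyses will be conducted".

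**SAP.** Section 3.3 redefines the PD endpoint as % inhibition at Days 14 and 28 and gives the population-level summary as "Treatment means for observed values and for percent inhibition from baseline". Section 12 plans "Descriptive statistics (including GM and gCV% for observed values and number of values BLQ) will be provided for observed values and %inhibition from baseline", on the natural scale, with figures of mean % inhibition with SD and individual profiles. It sets BLQ values to 0 in descriptive statistics. Section 7.1 adds the median, minimum, maximum and number BLQ, and calculates GM and gCV% only from quantifiable values above 0. On departures from the protocol, section 13 says: "Currently, no changes from the protocol-specified analyses are planned". Section 2 makes the SAP prevail where the documents differ and sends the differences to the CSR.

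**The concern.** Because the SAP prevails, its silence in effect removes the PD model. The trial would then report separate arm summaries for an objective worded as a comparison, leaving readers to subtract one small-arm mean from another with no measure of uncertainty. The separate PK/PD plan announced in SAP 11.1.4 covers exposure-response and does not supply the missing contrast.

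The SAP does not treat modelling as unworkable at this size. Section 9.1 gives spirometry an ANCOVA, and section 9.2 gives the CFQ-R respiratory scale a repeated-measures model, both with differences from placebo and 95% CIs. Protocol 9.4.4 planned only listings and summaries for FEV1 and CFQ-R. The endpoints with a planned model lost it, and those without one gained it.

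There is also a question of scale. Individual % inhibition is 100 × (1 − post/baseline). It cannot exceed 100 and has no lower bound, so one participant whose marker rises several-fold can pull down the mean of a seven-person arm.

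**Working it through.** **1. The two plans side by side**

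| Element | Protocol 3 and 9.4.4 | SAP 3.3 and 12 |
|---|---|---|
| Endpoint | Change to Day 14, to Day 28 and over 28 days | % inhibition at Day 14 and Day 28 |
| Summary | Between-group comparison, 95% CI | Mean per arm |
| Method | Linear model with covariance pattern, if sample sizes suffice | Descriptive statistics and figures |
| Declared in SAP 13 | – | No |

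**2. Check of the log-scale formula.** The documents give no precision figure for PD, so I first reproduced SAP Table 2 for PK. The multiplier is exp(t(0.975, N−1) × √ln(1+gCV²) / √N). With N = 7, t = 2.447 and gCV 30, 40 and 50%, it gives 1.312, 1.428 and 1.548, as stated.

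**3. Arithmetic illustration, n = 7.** Six participants have 60% inhibition (fold change 0.4) and one has a 5-fold rise (−400%).
- Arithmetic mean: (6 × 60 − 400)/7 = −6%.
- Geometric: 100 × (1 − exp[(6 ln 0.4 + ln 5)/7]) = 100 × (1 − 0.574) = 43%.
- Median: 60%.

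**4. Size of the distortion.** Assume a log-normal fold change with median 0.5 (true median inhibition 50%) and log-SD s. The documents give neither value. The expected mean % inhibition is 100 × (1 − 0.5 × exp(s²/2)). The last three columns give the chance that a summary of seven participants falls below 25%:
- arithmetic mean: by simulation;
- geometric version: P(Z > √7 × ln 1.5 / s);
- median: the binomial chance that at least 4 of 7 exceed a fold change of 0.75, each with probability P(Z > ln 1.5 / s).

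| s | gCV | Expected mean | Arithmetic mean <25% | Geometric <25% | Median <25% |
|---|---|---|---|---|---|
| 0.3 | 31% | 48% | <0.1% | <0.1% | 0.2% |
| 0.5 | 53% | 43% | 7% | 2% | 4% |
| 0.8 | 95% | 31% | 33% | 9% | 13% |
| 1.0 | 131% | 18% | 48% | 14% | 19% |
| 1.2 | 179% | −3% | 60% | 19% | 23% |

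**5. What a restored contrast would deliver.** Assume a true dose-to-placebo ratio of 0.40. The 95% CI is 0.40 multiplied and divided by exp(t × s × √(1/n₁ + 1/n₀)), with s² = ln(1+gCV²). The residual df is 21 for arms of 7/7/7/4 (t = 2.080) and 29 for 7/7/7/7/6 (t = 2.045).

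| gCV (assumed) | 7 vs 4 | 7 vs 6 |
|---|---|---|
| 50% | 0.22–0.74 | 0.23–0.68 |
| 100% | 0.14–1.18 | 0.16–1.03 |
| 150% | 0.10–1.65 | 0.12–1.38 |

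This simplified two-arm contrast at one visit ignores any gain from baseline adjustment or repeated measures, and any loss from missing sputum.

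**The case against.** The best defence is that little was promised. The model was exploratory and conditional, section 9.4.1 disclaims inferential analysis, sputum is not required from participants who cannot provide it, and placebo has about 4 participants, or 6 with the 65 mg cohort. A sponsor may choose descriptive PD in a feasibility-sized Phase 2a trial, and SAP 2 lets the SAP prevail. All of this stands. It shows that the loss is an imprecise exploratory estimate. It does not explain why SAP 13 is silent, or why FEV1 and CFQ-R keep a contrast under the same sample sizes.

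The second defence concerns scale, and it largely stands. A reader might infer that the PD output as a whole would mislead. The documents do not support that: the same tables carry the median, range and number BLQ, and individual profiles are plotted. The median in step 4 behaves nearly as well as the geometric version. The criticism is confined to the arithmetic mean, which is the estimand summary and the plotted value. At a log-SD of 0.3 to 0.5 it is only slightly to moderately off.

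A third objection is that a log-scale model could do harm. With BLQ set to 0 the log does not exist, and leaving BLQ values out would drop the strongest responders. Protocol 2.3.1 and 4.3 describe sputum NE falling below quantification in the earlier bronchiectasis study, so this may well arise here. The objection is sound, and the fix has to include a BLQ rule.

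**Conclusion.** The point holds as an undeclared departure from a conditional protocol analysis. The SAP specifies no PD estimate against placebo, no CI and no 28-day endpoint, and its own list of changes does not say so. That part rests on the text alone.

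The scale issue is secondary. That % inhibition is bounded on one side only is certain; how much this matters is not known. For a true 50% inhibition the expected mean runs from 48% (log-SD 0.3) to −3% (log-SD 1.2). All these log-SDs are assumptions, and nothing in the documents says which applies to blood or to sputum.

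A reader might also infer that a hypothesis test or a dependable efficacy signal has been lost. It has not: the protocol rules out testing, and step 5 shows that an assumed 60% reduction could still have an interval crossing 1 at a gCV of 100%. The value of the contrast is that it shows this uncertainty, which bare arm means hide. The SAP should be corrected, but the primary PK and safety objectives are unaffected.

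**What to change.** 1. In SAP 12, under the protocol's sample-size condition, restore a repeated-measures model for ln(post/baseline), separately for each marker and for blood and sputum. Include ln(baseline), treatment, visit and treatment-by-visit. Add CFTR stratum only if data allow, since the first three cohorts have about one non-modulator placebo participant.
2. Report each dose versus pooled placebo as a geometric mean ratio with 95% CI, at Day 14, at Day 28 and averaged over both. The protocol does not define change over the 28 days; this average is one workable reading and should be stated as such. Align SAP 3.3.
3. Prespecify a BLQ rule for the log scale, for example a fixed fraction of the LLOQ or a censored-data model, with a sensitivity analysis. Cover BLQ baselines, where a value of 0 leaves the fold change undefined. Reconcile SAP 12 (BLQ as 0) with SAP 7.1 (numeric part of values recorded with <).
4. Make 100 × (1 − geometric mean fold change), or the median, the main summary and plotted value. Keep the other statistics.
5. If the model or the 28-day endpoint is dropped on purpose, list it in SAP 13 with the reason.

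The cost is SAP text and standard code on samples already scheduled, settled before database lock. The downside is wide intervals, which must be labelled as exploratory estimation.
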